Evaluation Goal:

To evaluate the safety and acceptability of the ShangRing device for nonsurgical circumcision in routine clinical settings, as a part of a comprehensive HIV prevention program for males in VMMC programs.

Evaluation Endpoints:

Primary Endpoint: the proportion of males experiencing mild, moderate and severe adverse events (AEs) associated with ShangRing circumcision procedures, including both intra- and post-operative events, and all device-related malfunctions (e.g., early spontaneous detachment).

Secondary Endpoints:

- Training needed for proficiency using the ShangRing device, including number of procedures to become fully proficient at applying and removing the ShangRing device.
- Client and provider acceptability, client satisfaction, and duration of procedure.
- The percentage of clients clinically healed 49-52 days post-placement of the ShangRing device, and the time at which point all clients are clinically healed.

Evaluation Design

Training Phase: this phase will be used to evaluate the training requirements for implementation by mid-level providers, to preliminarily assess acceptability to providers, and to monitor logistical needs. Each clinician will perform no fewer than 10 ShangRing device placements, and 5 ShangRing removals before start of the next phase (implementation pilot).

Implementation Pilot: following the training period, 575 male clients will be recruited to undergo circumcision with the ShangRing device in the context of routine service delivery.

Data will be collected at up to at least 5 points in time: at enrollment and device placement (day 0), at device removal (day 7), during a follow-up phone call (day 10), in-depth qualitative interviews for 50 purposefully selected clients (day 28), at an in-person follow-up visit to assess wound healing (day 49), and at subsequent weekly visits to assess healing for those not completely healed at day 49.

Upon completion of the implementation pilot, the data will be analyzed and used to assist with policy decisions and recommendations on ShangRing use in adult male circumcision programs.

Section C: Protocol

Introduction

Voluntary Male Medical Circumcision (VMMC), VMMC Devices and ShangRing

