 - A description of each adverse event by type, severity, time of detection (days post-application and/or post-removal) captured as date AE is diagnosed, clinical management, and resolution. The likelihood of relatedness to having undergone VMMC and relatedness specifically to the ShangRing device will be determined. AEs will be defined using the definitions in the second edition of the VMMC Adverse Event Action Guide.²⁴ These are specific to each AE type, but in general:
 - Mild: classification indicates minimal or no intervention is required beyond reassurance and observation;
 - Moderate: classification relates to those AEs that are neither mild nor severe, require intervention, and are usually managed on-site;
 - Severe: classification requires extensive intervention with referral or specialist input.
 - Note: a Serious Adverse Event (SAE) is a standard definition used across many types of interventions. In the context of VMMC, all AEs that meet criteria for severe should also be classified as SAEs. In addition, SAEs also include any event that:
 - Results in death

- Is life threatening
- Requires intervention to prevent permanent disability or incapacitation (including deformity), or results in permanent disability or incapacitation (including deformity)
- Requires hospitalization or referral to a specialist for higher level care or intervention.
- (Note: device displacement is included as an AE both in the moderate and severe classifications – see Appendix XV).

Secondary Endpoints

- Determine the training needed for proficiency, including number of procedures required under supervision to become certified as fully proficient. This will involve analyzing AE rates stratified by during training and post-training in addition to overall.
 - Determining whether various cadres are trainable as safe providers. This would involve analyzing AE rates stratified by provider cadre.
- Document client acceptability and satisfaction, to be measured by the following:
 - Time for client to return to normal activity, including work and routine tasks.
 - Clients' opinions of convenience (having device applied, 'wearing' the device for a week, and returning for device removal), acceptability, cosmetic result, and whether they would recommend VMMC, and specifically the ShangRing VMMC option to others.

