ShangRing devices and medical instruments for placement and removal will be supplied to each partner at the beginning of the evaluation pilot. Partners will be responsible for further distribution to their pilot sites. Depending on actual consumption, disbursed supplies may be recalled for redistribution to match supply with demand at each site. A total of 750 devices will be purchased in various sizes to allow for the 575 procedures to be performed, as well as those performed during the training phase.

Evaluation Phases

Training Phase

During the training phase, clinicians at participating sites will be trained in the use of the ShangRing device by “master trainer” clinicians who have previous experience with the ShangRing device. This training phase will be used to evaluate the training requirements for implementation by mid-level providers, and to preliminarily assess acceptability to providers and clients and monitor logistical needs. Each clinician will perform no fewer than 10 ShangRing device placements, and 5 ShangRing removals before the start of the implementation pilot. Between 8 and 12 providers will be trained, meaning the number of clients receiving ShangRing during this time will be approximately 80-120. The clinicians trained in the master trainers will then train midlevel providers at the participating sites (anticipated to be another 2-4 providers at each site). Implementation pilot data will be collected from the clients receiving circumcisions with the ShangRing device during the training phase.

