Private spaces in the clinic sites will be used to privately administer interviews and counseling, and provide service referrals. Only evaluation staff, investigators and clients will be granted access to these spaces during the times the evaluation is being conducted. All documents and materials related to the evaluation will be stored in a locked cabinet in a locked office. Electronic data and files will be maintained on password protected computers, used only by the evaluation team.

Clinic Space and Circumcision Area

The ShangRing procedures will be conducted in a sterile, surgical environment, at sites in Shinyanga, Tanzania.

Staff Training

Physician Training

Physicians from Tanzania will be connected to physicians from countries with previous ShangRing experience (i.e. Kenya, Malawi, Uganda, Zambia) who have been trained and certified as Trainers of Trainers (TOT) at Ningbo Hospital, China, for training to be performed either in Tanzania, or the trainer's home country. The training will follow the framework outlined by expert consultants from the Department of Urology at the Weill Cornell Medical College. Studies suggest that newly trained providers needed to perform a minimum of 7 ShangRing procedures during training in order to be considered competent with the device.³² Therefore, each trainee physician will perform at least 10 placements of the ShangRing device, and five removals as part of their training. All ShangRing procedures in this group will be closely monitored and tutored by the TOTs. The trainee physicians will act as both operator (the physician applying the ShangRing device) and as assistant alternately. The trainee physicians will also be trained on device removal and AE management. All routine follow-up, including the resolution of any adverse events, will be adhered to based on standard practice. All client data collected during the training phase will be included in the final analysis.

The ShangRing experienced physicians will use a checklist to document each trainee's proficiency. The checklist will include the following proficiencies:

- Determination of suitability for circumcision using ShangRing
- Selection of the correct ShangRing size
- The placement procedure and subsequent removal of the foreskin
- Prevention and management of pain
- Removal of the ShangRing device
- Post-circumcision follow-up of clients, including assessment of wound healing and identification and management of adverse events

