When each physician's ShangRing skills are found acceptable by passing a training course and theoretical, practical and clinical tests, s/he will be certified by the training provider as competent. The newly certified Tanzanian physicians will then assist in training mid-level providers (registered and enrolled nurses) in Tanzania.

Mid-Level Provider Training

An integrated team, led by the TOTs and assisted by the recently ShangRing trained Tanzanian physicians, will conduct the training for mid-level providers (defined as registered and enrolled nurses) in Tanzania. In this phase of evaluation activities, each trainee mid-level provider will also successfully perform 10 placements and 5 removals before being deemed competent. All ShangRing procedures in this group will be closely supervised and

tutored by the integrated training team described above. When each trainee provider's ShangRing skills are found acceptable by passing a training course and theoretical, practical and clinical tests, s/he will be certified by the integrated training team as competent and permitted to participate in the evaluation as a ShangRing evaluation provider. Additionally, by having the recently trained Tanzanian physicians assist in the training of mid-level providers, the Tanzanian physicians will be better able to conduct future trainings in the event of ShangRing scale-up. All outcomes data during the training phase will be collected per the protocol as part of their training, but will not be included in the analysis.

Additional Staff Training

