Interested males will be informed about: (a) the evaluation requirements, (b) their potential role in the evaluation, (c) the ShangRing circumcision method, and (d) the evaluation procedures. Those males interested in participation will continue with the enrollment process, which includes the following:

- Administration of informed consent
- Confirmation of eligibility through inclusion/exclusion criteria
- Assignment of the client number
- Administration of evaluation questionnaires and case report forms (CRFs) to collect needed information
- Review of medical and medication history
- Completion of a physical examination, including a genital exam, and photography
- Collection of contact information from the client

Males with contraindications for circumcision or device circumcision will not be permitted to participate and they will be referred for standard surgical circumcision, if appropriate.

If a man cannot be circumcised on the day of screening and enrollment, he will be asked to return to the site within seven days to complete the circumcision procedure. Men who do not return within one week of screening will have to undergo re-screening to be enrolled.

Recruitment for the implementation pilot will begin as soon as the providers participating in the ShangRing training are considered competent in its application as demonstrated by passing knowledge and theory based tests, have performed no fewer than 10 placements and 5 removals (approximately 80-120), and deemed ready by the training clinicians to perform ShangRing circumcisions.

Written Informed Consent

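### The training rule bounds the proficiency count below at 10 placements and 5 removals, so it can show that trainees need more but not that fewer would suffice

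*Protocol*

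**What the plan says.** The Executive Summary lists training needed for proficiency as a secondary endpoint, "including number of procedures to become fully proficient at applying and removing the ShangRing device". Secondary Endpoints in the body ties the count to certification: "including number of procedures required under supervision to become certified as fully proficient". It then names an analysis: "This will involve analyzing AE rates stratified by during training and post-training in addition to overall".

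Four places set a minimum:
- Training Phase: "Each clinician will perform no fewer than 10 ShangRing device placements, and 5 ShangRing removals before the start of the implementation pilot".
- Physician Training: "each trainee physician will perform at least 10 placements of the ShangRing device, and five removals as part of their training".
- Mid-Level Provider Training: "each trainee mid-level provider will also successfully perform 10 placements and 5 removals before being deemed competent".
- Recruitment and Enrollment of Clients makes it a condition for starting the pilot that providers "have performed no fewer than 10 placements and 5 removals (approximately 80-120" clients in total, and that the trainers judge them ready.

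Physician Training derives the minimum from studies suggesting that new providers "needed to perform a minimum of 7 ShangRing procedures during training in order to be considered competent". It also describes a proficiency checklist for each trainee, but gives neither how often it is completed nor a criterion for being proficient. Certification further requires theoretical, practical and clinical tests.

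**The concern.** An endpoint that asks how many procedures a provider needs should be able to return a small answer as well as a large one. Here the answer is cut off from below by the rule that governs training. The reported number for a trainee who was fluent at the fourth placement is the same as for one who became fluent at the tenth.

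The Justification for Evaluation says that the results will inform Ministry policy, provider training included. A median of 10 placements and 5 removals could be read there as an empirical finding about learning, when it is largely the minimum that the protocol imposed. The named AE comparison does not fill the gap, because it contrasts two periods and does not follow a trainee from procedure to procedure.

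**Working it through.** **Reproducing the plan's figure.** Training Phase expects 8 to 12 providers with at least 10 placements each: 8 x 10 = 80 and 12 x 10 = 120. This matches the stated 80-120 clients.

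**What the count can record.** Let T be the placements a trainee truly needs and R the removals. With certification only after the minimum, the observed counts are max(T, 10) and max(R, 5). Every T from 1 to 10 gives 10. To show the effect, T was simulated with an assumed standard deviation of 2 between trainees (20,000 draws; neither the means nor the SD comes from the protocol):

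| Assumed mean of T | Observed mean | Observed median | Share with T of 10 or fewer |
|---|---|---|---|
| 3 | 10.00 | 10 | 100% |
| 5 | 10.00 | 10 | 99.7% |
| 7 | 10.05 | 10 | 96.1% |
| 10 | 10.78 | 10 | 60.2% |
| 12 | 12.15 | 12 | 23.0% |

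True means of 3, 5 and 7 are practically indistinguishable. A mean of 12 is visible. The count is informative above the minimum only.

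**What the AE comparison can show.** Inputs: 2% AE rate (Sample Size section), 80-120 training clients, and 495-455 later clients (Table 2).
- Expected training clients with an AE at 2%: 0.02 x 80 = 1.6; 0.02 x 120 = 2.4.
- Of these, in placements 8 to 10 (three tenths of the total): 0.02 x 24 = 0.48; 0.02 x 36 = 0.72.
- Exact 95% interval if two such clients are seen: 2/80 gives 0.3-8.7%; 2/120 gives 0.2-5.9%.

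Power of a two-sided 5% Fisher exact test against 2% after training, as a yardstick (the protocol specifies no such test):

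| True training AE rate | 80 vs 495 | 120 vs 455 |
|---|---|---|
| 4% | 19% | 21% |
| 7.6% | 67% | 76% |
| 10% | 87% | 93% |

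The 7.6% is the moderate and severe rate in the ShangRing arm of the Kenyan comparison cited under Potential Harm: (14 + 1)/197 = 7.6%. It is used only as a reference level.

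The comparison could therefore flag a large training excess and would probably miss a doubling. Whatever it shows, its dividing line is the end of training, which comes at the tenth placement or later. It cannot say at which procedure proficiency was reached.

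**Other training data.** Analysis Overview tracks training-phase procedure times but does not compare them, and its first-15 versus last-15 comparison uses post-training procedures only. Mid-Level Provider Training collects outcomes from that phase and leaves them out of the analysis. The tests, interviews and provider survey describe the quality of training; none yields a procedure number.

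**The case against.** The best reply is that the protocol asks a narrower question. The body's endpoint is the number of supervised procedures needed for certification. A trainee can fail tests, or need extra attempts to reach 10 successful placements, and then records more than 10. Whether 10/5 is enough is observable and useful to the Ministry. That stands, and for that reason the count is bounded below, not fixed.

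A reader might go further in three directions that the document does not support:
- That the evaluation sets out to test the cited figure of 7 and cannot. The protocol states no such aim; it uses 7 to justify the minimum, and a margin above a cited minimum is not an error.
- That almost every trainee will record exactly 10 however fast they learn. The simulated shares rest on assumed means and an assumed SD, and slow learners do move the count.
- That the AE comparison cannot detect any plausible training effect. Power is 67-76% at 7.6% and 87-93% at 10%. The 1.6-2.4 expected clients also presuppose no training excess.

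It can also be said that 80-120 undercounts training placements, since Training Phase anticipates another 2-4 providers at each of the two sites. At 10 placements each, that is 40 to 80 more. Mid-Level Provider Training, however, keeps mid-level training outcomes out of the analysis, and more placements would still not locate a procedure number.

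Finally, checklist frequency and scoring may sit in the SOP manual or training materials, and every training procedure is already closely supervised. If the checklist is completed each time, much of the fix is in place. The protocol neither says so nor names a criterion.

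**Conclusion.** The point holds in a limited form. As fixed in the protocol, the certification count is max(true need, 10) for placements and max(true need, 5) for removals. It can show that the minimum was too few for some trainees; it cannot show that fewer would have sufficed, and a result near 10 would mostly reflect the rule. The bound is written as an explicit gate on competence for mid-level providers. For physicians it follows from the minimum set elsewhere, with the same effect.

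The bound itself needs no assumption beyond the rule being followed. The AE figures assume a 2% post-training rate and the client numbers in Table 2. This concerns a descriptive secondary endpoint in about 8-12 providers, or somewhat more. The primary AE endpoint and the sample size are unaffected, and a training minimum is not itself a fault. The change is still worth making before training starts, because a record not taken at each procedure cannot be rebuilt at analysis.

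**What to change.** Leave the 10/5 minimum unchanged, and add to Staff Training and Secondary Endpoints:
1. The supervising trainer completes the Physician Training checklist after each supervised placement and each supervised removal, for physicians and mid-level trainees alike, using the items relevant to that procedure.
2. A proficiency criterion is prespecified. One form would be all relevant items passed unassisted on consecutive procedures, with the run length for the sponsor to choose.
3. The first procedure at which the criterion is met is reported by cadre, for placements and removals, separately from the certification count.
4. The certification count is reported as bounded below at 10 placements and 5 removals.
5. AE rates during and after training are labelled descriptive and not presented as an answer to the number of procedures needed.

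The cost is a few minutes of trainer time per training procedure, from trainers who already supervise every case, plus entry of the extra checklists. If the checklist is already completed each time, only the wording and the criterion are new. No additional clients or procedures are needed.
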